### 7.1.4 Shoulder stability tests for age matched controls (not for screening)

	CRITERIA	YES	NO	Type e.g. (L)
1.	Please make note of any clinical findings of - Apprehension (A) - Guarding (G) - Laxity (L)	1a. Sulcus (inferior) 1b. Anterior shift load 1c. Posterior shift load 1d. Apprehension relocation		

## 7.2 Consent

Three different consent/assent forms have been developed.

For participants below 9 years old, very simple language was used with two tick boxes that indicate acceptance (smiley face) or decline (frowning face) to demonstrate feelings about taking part instead of initial boxes. This document's readability level was also checked with two children (7 and 8 years old), who found it understandable.

For ages between 9-15, their assent form contains simple questions with simple YES or NO answer instead of initial boxes. This document's readability level was checked by a Public Involvement and Engagement group (CRN West Midlands) and different children of appropriate age groups.

Those above 16 years and parent/guardians, their consent form language level was checked with two teens (18 and 17 years old).

Once participants and their parents/guardians have expressed an interest in the study, the researcher will spend time discussing the research with participant and parents/guardians to ensure that all of their questions and concerns are addressed.

During the visit, the participants and their parent/guardian will be provided with an additional opportunity to ask questions. Once that is completed, the researcher will provide the consent form to parents/guardians, and will explain the purpose of the appropriate assent/consent form. Participants will fill out the assent form with the presence of parents/guardians and the researcher.

All developed forms language level was done using Microsoft Word Flesch-Kincaid tool to ensure that they meet the language level of their target participants.

### 7.3 Methodology/ Measurement protocol

Following the consent/assent process the following methodology/ protocol will be used to collect the data required for meeting the study objectives. For children with shoulder instability, the affected arm will be measured. For children with no instability the dominant hand will be measured.

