#### **6.2.2 Exclusion criteria**

- Any previous presentation to a health care professional with a diagnosis of shoulder instability
- Children with a previous shoulder injury within the last 3 months on the arm being assessed that has not resolved
- Children with co-existing neurological pathologies or deficits
- Children who have had a previous surgical intervention on the arm being assessed
- Children currently undergoing or awaiting medical management, diagnostic investigations or rehabilitation on the arm being assessed

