### 7.4 Instability history

For participants identified as being eligible ONLY, the follow up questions below should be asked

	FOLLOW UP QUESTIONS		RESPONSE	
F1.	Time since last episode of instability			
	Side of instability		LEFT	RIGHT
	Dominant hand		LEFT	RIGHT
F2.	Most recent episode of instability	Partial (subluxation)		
		Full (dislocation)		
F2.	Reported direction of instability	Anterior	YES	NO
		Posterior	YES	NO
		Multi-directional	YES	NO
F2.	Previous instability episode types	Partial (subluxation)		
		Full (dislocation)		
F2.	Number of instability episodes	Partial (subluxation)		
		Full (dislocation)		

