## 7.7 Movements for data capture

### 7.7.1 Grip Strength

Participants will have their grip strength tested using a handheld dynamometer. The total repetitions **will not exceed 3** for each activity and will be broken up into **3 sets of 1 repetition each side**.

- **Testing limb**
  - affected and unaffected arm [children with instability]
  - left and right/ dominant and non-dominant arm [children without instability]
- **Starting position** – Participant in standing. Elbow flexed to 90° with hand in thumbs up position with handheld dynamometer.
- **Movement task** – Participants will be instructed to squeeze the handheld dynamometer as hard as they comfortably can for no longer than 5 seconds

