### P1. Flexion

- **Testing limb**
  - affected arm [children with instability]
  - dominant [children without instability]
- **Starting position** – Participant in standing. Palmar surface resting on the lateral aspect of their thigh (in keeping with the midline of the body in the coronal plane).
- **Movement task** – Participants will be instructed to lift their arm out in front of them as high as they possibly can and then return it to the starting position.

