#### 7.7.4 Movement under load

- **These will not exceed 6 repetitions for each i.e. 2 sets of 3 repetitions**

Participants will perform the movements outlined below under a loaded condition using a self-selected weight. The participants will be provided with a series of weights from which to choose and advised to select a weight that allows them to complete the movements comfortably.

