### 8.3 Statistical analysis plan

The aim of this study is to identify factors responsible for recurrent shoulder instability in children. To meet the main aim, the following objectives, need to be met. The methods of analysis used to meet the study objectives have been reported below.

The analysis of measurement units will inform the main study objective and secondary objectives.

- **Kinematic** data such as joint angles and displacements – average range of movement values, as well as absolute minimum and maximum values will be reported for all functional tasks. For comparison purposes, descriptive statistics will be used to report the group behaviours and variability including means and standard deviations.
- **Kinetics** - force/strength – The range of force and strength values, as well as absolute minimum and maximum values will be reported for all functional tasks. For comparison purposes, descriptive statistics will be used to report the group behaviours and variability
- **Muscle activity patterns** - muscle activity (absence or presence), timing of muscle onset, percentage of maximum contraction and time of peak intensity will be used. This methodology is consistent with previously published research and is used for informing clinical decision making processes

The secondary research objectives used to address the main aim of the study are:

1. Validation of a 3D movement analysis protocol for measuring upper limb function in children with shoulder instability.
  - i) Individual variability (associated with of the measurement units outlined above) will be determined using the coefficient of variation for all data.
  - ii) The reliability and error associated with the protocol will be determined using the standard error of measurement for the measurement units outlined above. The reliability of the protocol will be determined through a sensitivity analysis investigating what effect perturbation of the virtual markers has on the outputs of the biomechanical model e.g. kinematics, position of the humerus
2. Obtain new data on muscle activity and movement patterns of children with and without shoulder instability
  - i) The method of analysis outlined above will inform this objective
3. Categorising clinical presentations of instability and identification of important factors for recurrent instability

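### Cases are measured on the affected arm and all controls on the dominant arm, so a normal dominance difference can leak into the case-control movement and sEMG comparison, and section 8.3 does not deal with it

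*Combined protocol and SAP*

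**What the plan says.** Section 7.3 sets the limb rule: "For children with shoulder instability, the affected arm will be measured. For children with no instability the dominant hand will be measured". The testing-limb lines of all seven movement tasks (P1 to P3, F1, M1 to M3) repeat it, so it is a deliberate rule and not a slip in one place.

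Sections 6.1.1 and 6.1.2 and the case screening form do not restrict the affected side. Section 7.4 records "Side of instability" and the dominant hand as separate left/right items. Age is the only stated matching factor.

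Grip strength (7.7.1) is the exception: both arms are tested in both groups.

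For kinematics, section 8.3 says that "descriptive statistics will be used to report the group behaviours and variability including means and standard deviations". For sEMG it lists presence or absence of activity and onset timing, and adds that "percentage of maximum contraction and time of peak intensity will be used". It mentions neither dominance nor the side measured.

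**The concern.** The comparison of children with and without instability is the substance of secondary objective 2. Under the limb rule the two groups can differ in two respects at once: instability, and the mix of dominant and non-dominant arms. A normal difference between the two arms could then be read as a feature of instability, in a study meant to find factors behind it.

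Analysis can repair this only in part. Cases can be split by dominance because section 7.4 records what is needed. No control supplies non-dominant movement or sEMG data, however, so cases affected on the non-dominant side have no like-for-like reference for these tasks.

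Several parts of the study are not affected:

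- The reliability work (standard error of measurement and marker perturbation) and the recurrence counts.
- Grip, where arms of the same dominance can be compared.
- The categorisation under objective 3, which concerns presentations of instability and would contain both kinds of arm whichever arm the controls use.

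**Working it through.** The plan gives no effect size, SD, alpha or power, so there is no figure of its own to reproduce. Everything below is in units of the between-child SD.

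**Inputs.** 15 cases and 15 controls (section 4). All controls are measured on the dominant arm (7.3). Assumed, because the documents give neither: k, the number of the 15 cases affected on the non-dominant side (q = k/15), and delta, the normal dominance difference. Delta and the case-control difference are each taken as unrelated to the other, so that the instability effect is the same on either arm.

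**Bias.** Let the control mean be μ and the true case-control difference τ. The case mean is then μ + τ − q × delta, and the contrast estimates τ − q × delta. The bias has size q × delta whatever the number of participants.

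**Standard error of the unadjusted contrast.** √(1/15 + 1/15) = √(2/15) = 0.365.

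| Assumption | Bias (SD) | Bias / SE |
|---|---|---|
| k = 0 or delta = 0 | 0 | 0 |
| k = 3, delta = 0.2 | 0.2 × 0.2 = 0.040 | 0.11 |
| k = 5, delta = 0.3 | 0.333 × 0.3 = 0.100 | 0.27 |
| k = 7, delta = 0.5 | 0.467 × 0.5 = 0.233 | 0.64 |
| q = 0.5, delta = 0.5 | 0.250 | 0.68 |

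If the long-run share were only 0.2, the chance of at least one non-dominant case among 15 would be 1 − 0.8^15 = 0.965. A mixed case group is therefore likely unless instability occurs almost always on the dominant side.

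**Can restriction to dominant-affected cases rescue the contrast?** With nd = 15 − k such cases, SE = √(1/nd + 1/15):

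- nd = 12: 0.387 (+6%)
- nd = 10: 0.408 (+12%)
- nd = 8: 0.438 (+20%)

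Compare mean squared errors. The unadjusted contrast has 2/15 + (k × delta/15)², the restricted one 1/nd + 1/15. They are equal when delta² = 15/(k × nd):

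- nd = 12, k = 3: √(15/36) = 0.645
- nd = 10, k = 5: √(15/50) = 0.548
- nd = 7 or 8: √(15/56) = 0.518, the smallest value for any nd from 1 to 14

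Below 0.518 SD the restricted contrast is always the worse estimator, so it serves only as a sensitivity analysis.

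**What matching the control arms gains.** Fit a linear model with group and arm dominance, with m controls measured on the non-dominant arm. Let T = k + m. The variance of the group effect is 1/[7.5 − (k − T/2)²/(T(30 − T)/30)]. With k = 7:

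- m = 0: 1/(7.5 − 12.25/5.367) = 0.192, SE 0.438 (+20%)
- m = 3: 1/(7.5 − 4/6.667) = 0.145, SE 0.381 (+4%)
- m = 7: 1/7.5 = 0.133, SE 0.365 (no loss)

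Full matching removes the bias at no cost in precision, and partial matching keeps most of that gain.

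**The case against.** The strongest objection is that no harm is shown. The documents give neither the share of non-dominant cases nor any sign that dominance matters in these tasks, and the middle scenarios amount to 0.11 and 0.27 of a standard error. The study is exploratory, has no single primary outcome, and plans only descriptive case-control summaries. Some outcomes may be less exposed: percentage of maximum contraction is scaled within the child, and the loaded tasks are done "under a loaded condition using a self-selected weight". All of this stands, and it keeps the point minor. It does not remove it, because under the present rule the controls give no movement or sEMG estimate of the dominance difference, so its size could not be judged from them afterwards.

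A second objection is that a fixed control arm is simple, gives a uniform reference dataset, and lets a control be screened at once. That is a real advantage. Control exclusions are defined by arm, for example "Children who have had a previous surgical intervention on the arm being assessed", so under matching a control can be fully screened only when the required arm is known, and case referrals run at about 2 a month. Matching would also leave few non-dominant control arms (about 3 to 7), which makes separate reporting by dominance thin; adjustment copes better.

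Two further limits are fair. The precision figures rest on the instability effect being the same on both arms. Section 7.3 also has no rule for a child with both shoulders affected, although matching can follow whichever arm was measured.

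**Conclusion.** The concern holds as a minor design weakness. The limb rule lets arm dominance differ systematically between the groups, and section 8.3 does nothing about it. The bias is q × delta: zero if all affected arms are dominant or dominance makes no difference, and from 0.04 to 0.25 SD across the non-zero scenarios shown, against a standard error of 0.365 SD. These sizes rest wholly on assumed values, so a possible bias is established and a material one is not. The reason to act is that it can be avoided without extra measurement for controls still to be seen, whereas the missing non-dominant control data cannot be recovered at analysis.

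**What to change.** **Sections 7.3 and 7.7, for controls not yet measured.** Choose the control's arm so that its dominance matches that of the age-matched case. If matching is at group level, choose arms so that the proportion of non-dominant arms is the same in both groups. In the control testing-limb lines of P1 to P3, F1 and M1 to M3, replace the dominant arm with the arm assigned under 7.3. Record which arm was measured, and state in 7.3 how the arm is chosen when both shoulders are affected.

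**Section 8.3.** Report the case-control kinematic and sEMG contrasts by, or adjusted for, dominance of the measured arm, stating the assumption of an equal instability effect on both arms. Compare grip between arms of the same dominance.

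**If some controls have been measured,** assign the remaining ones to bring the proportions together. **If all have been measured on the dominant arm,** keep the all-case contrast as the main one and state how many cases are affected on the non-dominant side. Add the comparison restricted to dominant-affected cases as a sensitivity analysis, and describe the other cases separately.

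**Cost.** Protocol wording, one analysis line and the amendment step in section 11. The number of arms, tasks, minutes and visits does not change. The practical drawback is later screening of some controls, which matching by proportion eases.

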### 7.4 Instability history

For participants identified as being eligible ONLY, the follow up questions below should be asked

	FOLLOW UP QUESTIONS		RESPONSE	
F1.	Time since last episode of instability			
	Side of instability		LEFT	RIGHT
	Dominant hand		LEFT	RIGHT
F2.	Most recent episode of instability	Partial (subluxation)		
		Full (dislocation)		
F2.	Reported direction of instability	Anterior	YES	NO
		Posterior	YES	NO
		Multi-directional	YES	NO
F2.	Previous instability episode types	Partial (subluxation)		
		Full (dislocation)		
F2.	Number of instability episodes	Partial (subluxation)		
		Full (dislocation)		

### 7.5 Nine point Brighton hypermobility score

One point is given for each of the side and test

	TEST DESCRIPTION		SCORE
B1.	Passively extend the fifth metacarpophalangeal joint $\geq 90^\circ$	L	
		R	
B2.	Passively oppose the thumb to the anterior aspect of the forearm	L	
		R	
B3.	Passively hyperextend the elbow to $\geq 10^\circ$	L	
		R	
B4.	Passively hyperextend the knee to $\geq 10^\circ$	L	
		R	
B5.	Actively place hands flat on the floor without bending the knees	L	
		R	
		Total	/9

## **7.6 Placement of marker clusters, surface electromyography (sEMG)sensors and identification of virtual markers**

### **7.6.1 Sequence of events for data collection**

[figure not shown]
[figure not shown]
- i. Bony landmark identification and mark up
- ii. sEMG placement identification and mark up
- iii. Skin preparation for sEMG
- iv. sEMG placement
- v. sEMG testing (recorded)
- vi. Marker cluster placement
- vii. Marking of cluster positions
- viii. Identification of virtual markers using pointer and static calibration (recorded)
- ix. Securing of required marker clusters and sEMG

### **7.6.2 Bony landmark identification**

[figure not shown]
[figure not shown]
The following bony landmarks will be palpated and marked for identification with the pointer following marker cluster and sEMG placement.

For consistency of bony landmark identification and marking participant should be seated with their hands resting on their lap.

Head position must be neutral i.e. no large degrees of flexion/extension

Location illustration	Description of identification of illustration
	
THORAX SEGMENT
 
 
C7 Spinous Process (C7) 
 
- C7 can be seen with flexion of the head and protrudes more dorsally than C6 and T1. With extension of the head C6 disappears first and C7 remains palpable for longer.
 
 
 
T8 Spinous Process (T8) 
 
- From either the proximal or distal reference points (below) Alternate with two palpating fingers and count from cranial to caudal to the 8th thoracic vertebrae
 
 
Reference points:
 
 
- T3 / T4 spinous process in line with spina scapulae
 
- T7 spinous process in line with angulus inferior scapulae
 
 
 
Incisura Jugularis (IJ) 
 
- Manubrium sterni is proximally bounded by the incisura jugularis. Cranial bowl-shaped limitation of the manubrium sterni (deepest point). Palpation/ identification of the point should be done from superior to inferior.
 
 
 
Processus Xiphoideus (PX) 
 
- Most caudal point of the sternum in keeping with the midline.
 
 
 

	
CLAVICLE SEGMENT
 
 
Art. Sternoclavicularis (SC) 
 
- Located bilaterally from the IJ, course from crano-medial to caudo-lateral. (protraction and retraction of the shoulder facilitate palpation)
 
 
 
Art. Acromioclavicularis (AC) 
 
- Front: follow the front of the acromion to medial until a discrete notch is felt (V-shaped to open anterior).
 
- Back: follow the top of the spina scapula and the back of the clavicle laterally to where the two bone pieces meet. A little further to the lateral side is the dorsal boundary of the AC joint.
 
 
 

[figure not shown]
	
SCAPULA SEGMENT
 
7. Processus Coracoideus (PC)
 
 
- In the fossa infraclavicularis (ventral) from medial to lateral palpation until one feels a medial, bony structure (only the top and medial side can be palpated). See CLAVICLE SEGMENT
 
- Palpation of the PC may be facilitated by protracting the shoulder girdle
 
 
8. Trigonum Scapulae (TS)
 
 
- Origin of the spina scapulae in line with the spinous process of T3 on the medial scapula edge. (spina goes to the latero-cranial). Palpate the midpoint of the triangular surface on the medial border of the scapula in line with the scapular spine
 
 
9. Angulus Inferior (AI)
 
 
- Follow the medial edge of the scapula caudally (most caudal point of the scapula, location at the level of the spinous process of T7)
 
 
10. Angulus Acromialis (AA)
 
 
- Follow the spina scapulae, from mid-caudal to latero-cranial until kink is felt in the dorso-lateral edge of the acromion (this rear corner is rectangular). Most laterodorsal point of the scapula
 

	
HUMERUS SEGMENT
 
11. Glenohumeral rotation centre (GH)
 
 
- Calculated via regression – with the participant's arm in abduction ask them to rotate their arm in a circular motion.
 
 
Forearm in supinated position
 
12. Lateral Epicondyle (LE)
 
 
- Palpable on the distal lateral side of the humerus (slight passive flexion of the elbow facilitates palpation).
 
 
13. Medial Epicondyle (ME)
 
 
- Palpable on the distal medial side of the humerus (slight passive flexion elbow).
 

[figure not shown]
[figure not shown]
	
FOREARM SEGMENT
 
Forearm in prone position – palpation should be done from distal to proximal
 
14. Radial Styloid (RS)
 
 
- Most caudal-antero point on the radial styloid
 
- Lateral edge of the radius leads distally into a depression. Palpate slightly proximal to the depression and the radial styloid is the palpable protrusion. Palpation easiest with radial deviation.
 
 
15. Ulnar Styloid (US)
 
 
- Most caudal-postero point on the ulnar styloid. Medial edge of the ulna leads distally into a depression. Palpate slightly proximal to the depression and the ulna styloid is the palpable protrusion. Palpation easiest with ulna deviation.
 

	
HAND SEGMENT
 
16. Styloid process of 3rd Metacarpal (MC3)
 
 
- Follow the third metacarpal on its dorsal side from distal to proximal. The small bone elevation on the base is the styloid process. Palpation easiest with maximum palmar flexion. (os capitatum lies in depression just proximal to styloid process of the 3rd Metacarpal)
 
 
17. Distal head of 2nd Metacarpophalangeal joint (MCP2)
 
 
- Palpate just distal to the 2nd metacarpophalangeal joint (these joints are easy to palpate on the dorso-lateral side in light flexion position or with longitudinal traction).
 
 
18. Distal head of 3rd Metacarpophalangeal joint (MCP3)
 
 
- Palpate just distal to the 3rd metacarpophalangeal joint (these joints are easy to palpate on the dorso-lateral side in light flexion position or with longitudinal traction).
 
 
19. Distal head of 5th Metacarpophalangeal joint (MCP5)
 
 
- Palpate just distal to the 5th metacarpophalangeal joint (these joints are easy to palpate on the dorso-lateral side in light flexion position or with longitudinal traction).
 

[figure not shown]
[figure not shown]
### 7.6.3 Surface electromyography (sEMG) placement

Muscle bellies will be identified and marked during the clinical examination. Skin preparation is required, using a conductive and slightly abrasive gel. Subjects with lots of body hair may need to have small patches of skin shaved at the site of the sensors. Small wireless sensors are placed over each muscle belly. These are held in place using a combination of double sided tape and elasticated bandage.

*The location of the bipolar sensor is always described as a point on a line between two anatomical landmarks. Where available electrode placement has been adapted from [SENIAM](#) guidelines or for cases [Criswell et al 2010](#)*

Placement illustration	sEMG electrode Placement
	
1. Middle Trapezius (listed on SENIAM as Upper)
 
Location: The electrodes need to be placed at 50% on the line from the acromion to the spine on vertebra C7
 
Orientation: In the direction of the line between the acromion and the spine on vertebra C7
 
Clinical test: Elevate the acromial end of the clavicle and scapula; extend and rotate the head and neck toward the elevated shoulder with the face rotated in the opposite direction. Apply pressure against the shoulder in the direction of depression and against the head in the direction of flexion anterolateral.
 
With hand resting by side
 
Prompts to participants for testing: “Shrug your shoulder up”
 
Guidelines: SENIAM

 
Source: Copyright © Clinical Resources, Inc.
	
2. Infraspinatus
 
Location: Palpate the spine of the scapula. Electrode placed parallel to and approximately 4 cm below the spine of the scapula, on the lateral aspect, over the infrascapular fossa of the scapula. Avoid placement over the posterior deltoid
 
Orientation: Parallel with the spine of the scapula.
 
Clinical test: Elbow bent to 90 degrees with lateral (external) rotation of the bent arm out to the side; abduction of the arm. Apply pressure to resist external rotation and abduction of the arm.
 
With their arm out to the side with elbow flexed
 
Prompts to participants for testing: “Push your arm out towards me”
 
Guidelines: Criswell et al 2010

 
Source: Copyright © Clinical Resources, Inc.
	
3. Triceps Brachii
 
Location: Electrodes need to be placed at 50 % on the line between the posterior crista of the acromion and the olecranon.
 
In some cases, the size of the participant's triceps relative to the sEMG electrode may not be sufficient to differentiate the heads of triceps. Therefore, a more central positioning may be used as a pragmatic approach to managing this and the cluster.
 
Orientation: In the direction of the line between the posterior crista of the acromion and the olecranon.
 
Clinical test: Extend the elbow while applying pressure to the forearm in the direction of flexion.
 
With their elbow bent
 
Prompts to participants for testing: “Straighten your elbow”
 
Guidelines: Criswell et al 2010

 
Source: Copyright © Clinical Resources, Inc.
	
4. Latissimus Dorsi
 
Location: Palpate the scapula. Electrodes are placed approximately 4 cm below the inferior tip of the scapula, half the distance between the spine and the lateral edge of the torso. They are
 
Orientation: Parallel to the fibres of Latissimus Dorsi which are oriented in a slightly oblique angle of approximately 25 degrees
 
With a cupped hand, supporting a flexed elbow
 
Prompts to participants for testing: “Push down and back in a rowing motion”
 
Clinical test: Extend, adduct, or medially rotate the arm. Participant to start arm externally rotated and in some forward flexion. Apply pressure to resist extension, adduction and medial rotation of the arm.
 
Guidelines: Criswell et al 2010

	
5. Posterior deltoid
 
Location: Centre the electrodes in the area about two finger breaths behind the angle of the acromion
 
Orientation: In the direction of the line between the acromion and the little finger.
 
Clinical test: Abduct the shoulder in slight extension, with the humerus in slight medial rotation. The humerus is placed in slight medial rotation in order to offload the posterior fibres. The anatomical action entails slight lateral rotation while pressure is applied against the posterolateral surface of the arm, above the elbow in the direction of adduction and slight flexion.
 
With their elbow flexed
 
Prompts to participants for testing: “Pull your arm back”
 
Guidelines: SENIAM

	
6. Anterior deltoid
 
Location: one finger width distal and anterior to the acromion
 
Orientation: In the direction of the line between the acromion and the thumb
 
Clinical test: Shoulder abduction in slight flexion, with the humerus in slight rotation. In the erect sitting position, it is necessary to place the humerus in slight lateral rotation to increase the load on the anterior fibres. The anatomical action of the anterior deltoid entails slight medial rotation while pressure is applied against the antero medial surface of the arm in the direction of adduction and slight extension.
 
With their elbow flexed
 
Prompts to participants for testing: “Push your arm forwards”
 
Guidelines: SENIAM

	
7. Pectoralis Major (clavicular head)
 
Location: For clavicular placement, palpate the clavicle. Electrode is placed on the chest wall at an oblique angle toward the clavicle, approximately 2 cm below the clavicle, just medial to the axillary fold
 
Orientation: at an oblique angle toward the clavicle
 
Clinical test: Flexion of the arm, abduction of the arm above 90 degrees, medial rotation, and horizontal adduction of arm.
 
With their elbow flexed to 90° and arm abducted and flexed
 
Prompts to participants for testing: “Push forwards out and in front of you”
 
Guidelines: Criswell et al 2010

Source: Copyright © Clinical Resources, Inc.

	
8. Biceps Brachii
 
Location: Electrodes need to be placed on the line between the medial acromion and the fossa cubiti at 1/3 from the fossa cubiti.
 
Orientation: In the direction of the line between the acromion and the fossa cubiti
 
Clinical test: Place one hand under the elbow to cushion it from table pressure and flex the elbow slightly below or at a right angle, with the forearm in supination. Press against the forearm in the direction of extension.
 
With their elbow flexed to 90°
 
Prompts to participants for testing: “Bend your elbow”
 
Guidelines: SENIAM

	
9. Common Flexor Origin
 
Location: About 3-5 centimetres from the elbow joint at distal ventral aspect of forearm. Assessor would ask subject to flex elbow to palpate flexors bulk.
 
Orientation: with the electrodes oriented in the direction of the muscle fibres which run longitudinally down the forearm.
 
Clinical test: Flexion of the wrist
 
Prompts to participants for testing: “Bend your wrist down”
 
Guidelines: Criswell et al 2010

Source: Copyright © Clinical Resources, Inc.

[figure not shown]
[figure not shown]
	
10. Common Extensor Origin
 
Location: About 3-5 centimetres from the elbow joint at proximal dorsal aspect of forearm. Assessor would ask subject to extend elbow and wrist, to palpate extensors bulk. Electrode is placed in the centre of the muscle bulk.
 
Orientation: with the electrodes oriented in the direction of the muscle fibres which run longitudinally down the forearm.
 
Clinical test: Extension of the wrist
 
Prompts to participants for testing: “Bend your wrist up”
 
Guidelines: Criswell et al 2010

--	---

[figure not shown]
[figure not shown]
[figure not shown]
*Source: Copyright © Clinical Resources, Inc.*

